# 3 Study Design

#### 3.1 General Design

This is a prospective, diagnostic accuracy study. The same study design is applied to each POC evaluation (sub-study) performed under this protocol. The study is conducted at several clinical study sites located in different countries, including two endemic African countries (DRC and CAR) and one newly affected European country (UK). Each index test is evaluated at all study sites. Each evaluation site may recruit study participants from one or more associated clinics.

Considering that the mpox outbreak situation (incidence) is subject to change, enrichment strategies to meet the study objectives may be discussed with single study sites and adopted at any time during the study, provided that specific go/no go criteria are met, and study validity and integrity can be preserved. Potential enrichment strategies considered are:

- Including close symptomatic contacts of a confirmed mpox case through contact tracing procedures
- 2. Frozen lesion and respiratory samples from FIND or local sample repositories, and/or same-day, fresh left-over specimens available in the local diagnostic laboratory may be used, provided they were collected from patients meeting the eligibility criteria.
- 3. Additional sites may be considered.

These strategies will allow to achieve the primary objective of the study and, most likely, to assess the usability of the POC under evaluation. Data collected, though, may not be sufficient/available to perform the subgroup analyses of the secondary objectives.

All study specimens and relevant information will be collected from enrolled participants on the day of recruitment. There will be no follow-up visits. Only PCR results will be communicated to the participant.

Point estimates of sensitivity and specificity, with 95% confidence intervals based on Wilson's score methods, will be calculated using a gold-standard PCR test as reference standard. In order to make the information on test performance available timely, a partial analysis will be performed every time the collection of data for each RDT has been completed at one site. This analysis will evaluate the primary for a given RDT at a specific site.

#### 3.2 Scientific Rationale for Study Design

A prospective design has important advantages over a retrospective design, including a participant sample that is better defined in terms of the participant's clinical characteristics, as well as standardized methods of sample collection and processing across sites and standardized methods of performing and interpreting the test(s) and reference standard procedure. In some circumstances, a prospective design is the only possible approach due to the intended use of the test (i.e. IFU requiring testing on fresh samples, immediately after sample collection) or disease under investigation. A prospective design is also well suited if the study is conducted during an outbreak.

However, given the unpredictability of the mpox outbreak, resulting in reduced disease incidence, a prospective design would be difficult to implement in a timely manner. In such circumstances, the only

Performance evaluation of Mpox point-of-care diagnostics

Protocol #PP008 Page 18 of 40

possibility to perform this study is through implementing enrichment strategies, such as including close contacts into the study, supplementing specimens collected prospectively with well-characterised specimens available in FIND or local sample archives, and/or including additional sites to conduct the evaluation.

# 3.3 End of Study Definition

A participant is considered to have completed the study after the specimens needed to perform the reference standard PCR test and the index test under evaluation have been collected and diagnostic results shared with the participant. All mpox DNA positive individuals will be linked to care as per country requirements.

The end of the study is defined as the date the minimum required number of mpox PCR positive and negative cases is reached per site.

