## (SITE to add specific setting details, if needed)

If a participant is screened and enrolled but is not able to provide the specimens required for the study, this participant will be withdrawn.

A participant can only be enrolled once in the study. Co-enrolment in multiple studies on the same day is allowed (i.e., where the subject is asked to provide similar specimens in parallel).

Prospective approval of protocol deviations to recruitment and enrolment criteria, also known as protocol waivers or exemptions, is not permitted.

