#### Steps to blind test readers and interpreters

- Index tests will not be run at the same time. One test evaluation will be completed before another
  index test evaluation can begin. This is aimed to reduce bias in interpretation of tests by results of
  another test.
- The Reference test and index test may be done on different days by different laboratory technicians in batches.
- The laboratory technician performing and reading the index test should be different from the one who performed the index test.
- Data entry into OpenClinica will be done by staff other than the laboratory technicians.

Laboratory technicians should not have access to OpenClinica data or patient files to minimize access to other test results and resulting bias.

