#### Index tests

Performance evaluation of Mpox point-of-care diagnostics

Protocol #PP008 Page 26 of 40

The samples for the index test (POC Ag or molecular) are processed by personnel trained by the test manufacturer directly, or FIND team trained by the manufacturer, at the testing location following the specific IFU provided by the manufacturer. The test result is recorded in the corresponding CRF alongside the picture of the developed POC Ag test as source data where applicable. The operator is blind to the reference test and other tests results, including other Ag RDTs that may be evaluated in parallel during the study.

If possible, all subjects enrolled for testing with a given novel POC test will have their PCR testing done with the same reference test done in the same institution.

Participants are diagnosed by their treating physician based on the reference PCR results performed on the diagnostic sample and clinical signs and symptoms; results of the POC tests are not communicated to the participants and not used for clinical management.

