# 8.2 Sample Size Determination

The sample size for this study per site is at least 30 positive and 30 negative samples for each index test evaluation based on U.S. FDA guidelines (9). Assuming that both the sensitivity and the specificity of the test are 90% this would result in a full width of 95% confidence interval of  $\pm 11\%$ , based on the formula 6.2 in Zhou et al (10).

Since the prevalence of the disease in these areas are unknown, an interim analysis will be performed to estimate the prevalence with its 95% confidence interval once the enrolment reaches 50 participants for each site. Following this, the lower bound of the confidence interval will be used to estimate the number of participants to be screened based on the formula 6.3 in Zhou et al. Assuming a lowest possible prevalence of 10%, 5%, and 1%, the number of participants to be screened to reach 30 confirmed cases with an 80% power would be:

10% prevalence: 348 to screen
5% prevalence: 697 to screen
1% prevalence: 3496 to screen

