#### 8.3 Populations for Analyses

For purposes of analysis, the following populations are defined in Table 5:

Table 5: Populations for analysis

Population	Description
Enrolled/intention-to-test (ITT)	All participants who sign the ICF
Evaluable/Per Protocol Population (PP)	All participants in ITT with valid reference and index test results

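### The end-of-study rule and the recruitment numbers count PCR results, but accuracy also needs a valid index result; separately, Sections 4.5 and 6.3 disagree on sequential or parallel testing

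*Protocol*

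**What the plan says.** **Target.** Section 8.2: "The sample size for this study per site is at least 30 positive and 30 negative samples for each index test evaluation". Sensitivity and specificity are both assumed to be 90%, and the stated precision is ±11%.

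**Stopping rule.** Section 3.3 sets the end of study as the date on which "the minimum required number of mpox PCR positive and negative cases is reached per site". The same section treats a participant as complete once specimens have been collected and diagnostic results shared; a valid index result is not required.

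**Recruitment numbers.** Section 8.2 gives 348, 697 and 3496 at prevalences of 10%, 5% and 1%, described as "the number of participants to be screened to reach 30 confirmed cases with an 80% power would be". Section 8.5 recalculates the number from the lower confidence limit of the prevalence once 50 participants at a site have PCR results.

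**Analysis set.** Section 8.3 defines the PP population as "All participants in ITT with valid reference and index test results", and Section 8.4.1 computes the accuracy endpoints on it. Section 4.3 allows an invalid index test to be repeated if enough sample is left. No expected rate of invalid results is given.

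**Testing sequence.** Section 4.5: "Index tests will not be run at the same time"; one evaluation is finished before the next starts. Section 6.3 blinds the operator to other results, "including other Ag RDTs that may be evaluated in parallel during the study". Section 3.4: "A participant can only be enrolled once in the study". Section 4.1 foresees up to three antigen and up to three molecular tests.

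**The concern.** The stopping rule and the analysis count different units. A PCR-positive participant whose index test stays invalid moves the site towards its end date but adds nothing to the sensitivity estimate. A site can therefore meet Section 3.3 with fewer than 30 positives available for the index test. The recruitment numbers have the same gap if they carry no allowance for invalid results.

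The testing sequence raises a second question: how many participants does a site need? If several tests are run in the same participants, one set of 30 + 30 can serve them all. If tests follow one another and nobody is enrolled twice, each test needs its own set. Sections 4.5 and 6.3 point in different directions, and Section 8.2 gives numbers for one set only.

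**Working it through.** **Inputs.** From the protocol: 30 positives and 30 negatives per index test and site, prevalence 10%, 5% or 1%, 80% assurance, accuracy 90% (all Section 8.2); up to 3 + 3 index tests (Section 4.1). Assumed here, because the protocol gives none: a final invalid rate *v* of 2%, 5%, 10% or 15%.

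**1. Reproducing the plan's figures.** Take the smallest N with (N·p − 30) / √(N·p·(1 − p)) ≥ 0.8416, the normal approximation to an 80% chance of at least 30 positives.

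- p = 10%, N = 348: (34.8 − 30) / √31.32 = 0.858. N = 347 just fails.
- p = 5% gives 697 and p = 1% gives 3496.

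All three match exactly, and the exact binomial gives 343, 687 and 3446. The half-width is 1.96 × √(0.9 × 0.1 / 30) = 0.107, the stated ±11%. The published numbers therefore cover one set of 30 PCR positives, with nothing added for invalid results or for more than one index test.

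**2. Chance of 30 evaluable positives at the planned N.** With 348 participants and 10% prevalence, each participant is an evaluable positive with probability q = 0.10 × (1 − *v*).

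| Assumed *v* | Expected evaluable positives | Exact P(at least 30) | N for 80%, same formula with q |
|---|---|---|---|
| 0% | 34.8 | 0.828 | 348 |
| 2% | 34.1 | 0.795 | 355 |
| 5% | 33.1 | 0.738 | 366 |
| 10% | 31.3 | 0.625 | 386 |
| 15% | 29.6 | 0.495 | 409 |

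The probabilities at 697 (5%) and 3496 (1%) agree to within about 0.01.

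**3. Stopping at exactly 30 PCR positives.** Expected evaluable positives are 30 × (1 − *v*), and the half-width is 1.96 × √(0.09 / (30 × (1 − *v*))).

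| Assumed *v* | Expected evaluable | Half-width (points) | PCR positives for 80% chance of 30 evaluable |
|---|---|---|---|
| 0% | 30 | 10.7 | 30 |
| 2% | 29.4 | 10.8 | 31 |
| 5% | 28.5 | 11.0 | 33 |
| 10% | 27.0 | 11.3 | 35 |
| 15% | 25.5 | 11.6 | 37 |

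**4. Negatives.** At 10% prevalence, 348 participants include about 348 × 0.9 = 313 negatives. Invalid results at these rates do not threaten 30. Negatives would be at risk only where prevalence is high.

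**5. Sequential or parallel.** If tests share participants, a site needs 30 positives, hence 348 participants at 10% prevalence. If each test has its own participants, it needs 30 × the number of tests: 60, 90 or 180 positives for two, three or six tests. The same formula then gives 666, 980 or 1911 participants at 10% prevalence. These figures carry no allowance for invalid results and no reduction for stored samples, and six tests is the upper limit in Section 4.1. The parallel wording in Section 6.3 names antigen tests only.

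**The case against.** **The practical loss is small.** This stands. Section 8.1 states that no hypothesis is tested, so precision is what counts, and the half-width moves by less than one point even at 15% invalid. Invalid tests may also be repeated, which lowers the final rate. The probabilities in step 2 measure whether the stated minimum is met, not damage to the estimate.

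**A reader might infer that the study could end after the first index test,** because Section 3.3 says only per site. The document does not support this. Section 3.3 gives no number of its own, and the minimum it refers to is set in Section 8.2, per site and for each index test. Section 3.1 treats each evaluation as a sub-study, and Section 8.4.1 plans a final analysis per test. Stating this in Section 3.3 would help, but it is not a contradiction.

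**A reader might infer that the 80% assurance collapses because the numbers are labelled as people to be screened,** when only some of those screened are enrolled. That needs an enrolment fraction the protocol does not give, and it assumes that recruitment stops at the planning number. In fact the study stops on case counts, and the number is recalculated from the lower prevalence limit. Section 8.5 counts participants with PCR results, so the label reads as loose wording for those tested.

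**Separate cohorts for every test are not stated.** This stands in part. They follow from combining Section 4.5 with single enrolment, and Sections 3.1 and 6.1 allow stored or left-over specimens. The conflict between Sections 4.5 and 6.3 remains.

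**Conclusion.** The mismatch of units holds. Section 3.3 and the Section 8.2 numbers count PCR results, accuracy uses PP participants, and the exact reproduction of 348, 697 and 3496 shows no allowance for invalid index results. The stated minimum of 30 evaluable positives per index test is therefore not secured, although the cost in precision is minor. The size depends on the assumed 2% to 15% invalid rate.

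The conflict on testing sequence is an internal contradiction with more practical weight. It leaves a site's requirement anywhere from one set of 30 + 30 to six, before any use of stored samples. Both points concern rules this protocol itself fixes for site conduct, so they should be corrected here. Neither invalidates the design.

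**What to change.** 1. **Sections 3.3 and 8.2, and the synopsis:** define the target and the end of study as at least 30 PCR-positive and 30 PCR-negative PP-evaluable results for each index test at each site.
2. **Sections 8.2 and 8.5, and the synopsis:** state an assumed invalid rate, use prevalence × (1 − invalid rate) in the formula, and label the result as participants enrolled and tested rather than screened.
3. **Sections 4.5 and 6.3:** reconcile them on whether index tests may be evaluated in parallel. Then state the participants per site that follow, and check that the planned 1 to 4 months of enrolment still fits.

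The cost is mainly wording. At 10% prevalence the planning number rises from 348 to 366 at 5% invalid (18 more) or 386 at 10% (38 more). At the stopping rule it means a few replacement positives, about 33 to 35 PCR positives instead of 30 at those rates.

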### 3.4 Study Population and Eligibility

Individuals ≥ 2 years of age with symptoms compatible to mpox (and/or specimens collected from them), as per national or WHO guidelines, attending healthcare facilities in Central African Republic, Democratic Republic of Congo, and United Kingdom.

## (SITE to add specific setting details, if needed)

If a participant is screened and enrolled but is not able to provide the specimens required for the study, this participant will be withdrawn.

A participant can only be enrolled once in the study. Co-enrolment in multiple studies on the same day is allowed (i.e., where the subject is asked to provide similar specimens in parallel).

Prospective approval of protocol deviations to recruitment and enrolment criteria, also known as protocol waivers or exemptions, is not permitted.

#### 3.5 Inclusion Criteria

Participants/specimens can be included in the study only if all the following inclusion criteria apply:

- Individual ≥ 2 years of age
- Meet case definition for a suspected case of mpox (as per national or WHO clinical case definitions; see Table 2)
- Provide written informed consent (by the participant or legal representative) and/or assent to participate in this study
- · Provide specimens for the study

#### Table 2. WHO case definitions for mpox (7)

# Suspected case

i. A person who is a contact of a probable or confirmed mpox case in the 21 days before the onset of signs or symptoms, and who presents with any of the following: acute onset of fever (>38.5°C), headache, myalgia (muscle pain/body aches), back pain, profound weakness or fatigue.

# OR

Performance evaluation of Mpox point-of-care diagnostics

Protocol #PP008 Page 19 of 40

ii. A person presenting since 01 January 2022 with an unexplained acute skin rash, mucosal lesions or lymphadenopathy (swollen lymph nodes). The skin rash may include single or multiple lesions in the ano-genital region or elsewhere on the body. Mucosal lesions may include single or multiple oral, conjunctival, urethral, penile, vaginal, or ano-rectal lesions. Ano-rectal lesions can also manifest as ano-rectal inflammation (proctitis), pain and/or bleeding.

#### AND

for which the following common causes of acute rash or skin lesions do not fully explain the clinical picture: varicella zoster, herpes zoster, measles, herpes simplex, bacterial skin infections, disseminated gonococcus infection, primary or secondary syphilis, chancroid, lymphogranuloma venereum, granuloma inguinale, molluscum contagiosum, allergic reaction (e.g., to plants); and any other locally relevant common causes of papular or vesicular rash.

#### 3.6 Exclusion Criteria

Participants are excluded from the study if any of the following exclusion criteria apply:

- Individuals with no visible rash or lesions
- Individuals who are in unstable condition as determined by their treating clinician

#### 3.7 Screen Failures

Screen failures are defined as participants who were eligible to participate in the study but are not subsequently enrolled in the study. A minimal set of screen failure information is required to ensure transparent reporting of screen failure participants to meet the Standards for Reporting of Diagnostic Accuracy Studies (STARD) requirements and to respond to queries from regulatory authorities. Minimal information includes demography, screen failure reasons, eligibility criteria.

# 4 Study Intervention

Study Intervention is defined as any investigational intervention(s), marketed product(s), or medical device(s) intended to be used with a Study participant according to the Study protocol.

#### 4.1 Investigational Product

The products under evaluation within this protocol are:

- POC Ag RDTs (up to 3)
- POC/near-POC Molecular assays (up to 3)

The list of potential products for evaluation is listed in Appendix 1.

Other tests may be considered as they become available and vetted through FIND selection process.

Instructions for use of the investigational products will be provided by each manufacturer and shared with sites.

Medical device incidents, including those resulting from malfunctions of the device (or IVD), must be detected, documented, and reported by the Investigator at each site throughout the study (see Appendix 3).

Performance evaluation of Mpox point-of-care diagnostics

Protocol #PP008 Page 20 of 40

# 4.2 Preparation/Handling/Storage/Accountability

#### Acquisition

Procurement of the investigational products will be done through FIND, who will coordinate shipments from the manufacturer. It is the responsibility of each Study site to maintain an updated inventory of the Study materials and to inform FIND immediately if additional materials are required.

The investigator or designee must confirm appropriate temperature conditions have been maintained during transit for the investigational product received and any discrepancies are reported and resolved before its use. Further details will be provided in the Study Manual.

#### **Installation and Storage**

Procedures for device installation and test kits storage and disposal will be described in the corresponding Instructions for Use (IFU) and manuals. For POC molecular tests, device installation will strictly adhere to manufacturers instruction, meeting all manufacturer and site-specific requirements as well for new equipment installation.

The investigational product must be stored in a secure, environmentally controlled, and monitored (manual or automated) area in accordance with the labelled storage conditions with access limited to the investigator and authorized site staff.

# **Test Handling and Performance**

Testing using the investigational products will be performed according to the manufacturer's instructions. Lesion, oropharyngeal, and blood samples, as per index test manufacturer's claim (e.g. lesion swab) from participants enrolled in the study will be processed with the investigational product and only authorized site staff will be responsible for processing.

#### **Accountability**

The investigator is responsible for Study intervention accountability, reconciliation, and record maintenance (i.e., receipt, reconciliation, and final disposition records).

#### **Export and Import Permits**

The Investigator at study site is responsible for making import permit applications in a timely manner. FIND logistics team will support providing documentation required from the Sponsor, usually including commercial invoice, packaging list and FIND donation letter. (SITE to amend accordingly)

# **Quality Control Check for Incoming Shipments**

Upon arrival of each new shipment of assays, the sites conduct an incoming quality check following sitespecific procedure. New lots may only be used after this quality check is successfully passed.

## **Local procurement**

Sites are responsible for assessing their needs and procuring any supplies, reagents and kits needed for the Study that are locally available and to include these costs in the study budget prior to study initiation.

#### 4.3 Minimisation of Error and Bias

# Participant/specimen selection

Spectrum bias will be minimized with the prospective study design. Enrolment is based on clearly defined eligibility criteria applicable to all sites. To ensure the validity and generalizability of study results, descriptive statistics based on participant characteristics (e.g. age, sex, days since symptom onset and PCR Ct values, as surrogate for viral load, etc.) to confirm diagnostic performance across different patient sub-groups will be reported.

Performance evaluation of Mpox point-of-care diagnostics

Protocol #PP008 Page 21 of 40

In the instance that enrichment strategies are employed to meet the required sample size, there is a risk of bias in the results as the performance of the tests may not reflect their true accuracy in the overall population (eligible for testing) but a subset with increased prevalence of mpox. Therefore, positive and negative predictive values will not be calculated if this was the case.

If frozen or same-day fresh left-over specimens will be used, spectrum bias will be limited by:

- Randomly selecting specimens from biobanks, considering the eligibility criteria and previous PCR qualitative result (positive or negative)
- Testing consecutive fresh left-over specimens from the diagnostic laboratory, considering only the eligibility criteria

